#### **6.2.1.5      Stopping Criteria for the Dose Escalation**

The dose escalation will stop when either:

- The maximum sample size for phase 1 (N=39) has been reached (section 11.2).
- There are 9 DLT-evaluable patients at the current dose level, and according to the mBOIN rules, the decision is to remain at the same dose level.
- The lowest therapeutic dose is disallowed (i.e., the starting dose is considered too toxic).

The dose escalation may also stop if there are 6 DLT-evaluable patients with  $\leq 1$  DLT on the current dose-level, provided that a higher dose-level has been evaluated and the number of DLTs on that higher dose-level leads to a de-escalation.

#### **6.2.1.6      Determination of MTD and RP2D**

The mBOIN-based MTD will be preliminarily estimated statistically as the dose level with the observed DLT-rate closest to the target toxicity level (i.e., 28%), as described in section 11.4.2.

After the mBOIN-based dose-escalation algorithm has been completed, the DMC and the Sponsor will determine the MTD and the RP2D, both of which may differ from the aforementioned preliminary statistical estimate. The RP2D cannot exceed the MTD.

The selection of the RP2D will be based on pharmacokinetic, pharmacodynamic, safety and efficacy data from Phase 1. The selection of RP2D will be informed by exposure-response analyses (cf. Section 11.4.9) and Frequency and severity of AEs will be balanced with any observed dose response for clinical activity. In the absence of compelling results as interpreted by the DMC and the Sponsor, the RP2D will be the highest dose administered that does not exceed the MTD. If there is evidence that a dose level lower than the MTD (which might not have been reached at this stage) has adequate clinical activity (whether determined by imaging data, pharmacodynamics endpoints, or predicted efficacious dose), the DMC and the Sponsor's safety committee may decide that the RP2D has been determined and that the dose escalation may be stopped.

Based on the available data, the DMC may recommend introduction of intermediate dose levels in between the pre-planned dose levels and may also suggest changing the dosing frequency.

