### 6.2.1.3 Dose Escalation Stages

The dose escalation phase will consist of 2 stages: the initial accelerated titration stage followed by a standard titration stage (Figure 6-1).

In the accelerated titration stage, patients will be recruited and treated in single-patient cohorts. These single-patient cohorts may optionally be expanded with up to 2 additional patients for the purpose of obtaining additional PK and/or pharmacodynamic data.

The initial accelerated titration stage will end, and the single-patient cohort mandatorily expanded with (at least) 2 additional patients once either:

- Dose level 3 is reached, or
- During the DLT evaluation period (28 days), a patient is observed with:
  - any grade  $\geq 2$  AE (excluding toxicities clearly related to disease progression or intercurrent illness), or
  - a protocol defined DLT (section 6.2.3).

whichever occurs first

This will mark the end of the accelerated titration stage and the beginning of the standard titration stage. Hereafter, patients will be allocated to dose-levels typically in cohorts of 3. As the mBOIN design allows cohort-sizes to vary, the actual cohort sizes may differ from 3.

In the standard titration stage, cohorts will be allowed to include only 2 patients who are evaluable for DLT, provided that none of the 2 patients have experienced any related, grade  $\geq 3$  AE during the DLT evaluation period.

If patients are withdrawn prematurely without having experienced a DLT, they will be considered non-evaluable and may be replaced.

In cohorts that include more than 1 patient in the dose escalation part, there will be sequential enrolment. At a particular dose level, there must be at least 3 days between the first dose of the first patient and the first dose of the subsequent patients in the same cohort.

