**Table 6-3 Phase 1 dose escalation rules based on the number of patients with DLTs**

Decision based on the number of patients with DLTs ( $N_{DLT}$ )	Number of patients evaluable for DLT at the current dose level							
	2	3	4	5	6	7	8	9
Escalate if $N_{DLT} \leq$	0	0	0	1	1	1	1	2
Remain on dose level if $N_{DLT} =$	NA	1	1	NA	2	2	2	3
De-escalate if $N_{DLT} \geq$	1	2	2	2	3	3	3	4
Disallow dose-level if $N_{DLT} \geq$	NA	3	3	4	4	4	5	5

**Abbreviations:** DLT = dose-limiting toxicity; NA = not applicable

It will not be allowed to escalate or de-escalate to dose levels on which an unacceptable level of toxicity has been observed; these dose levels are disallowed, as addressed by the last row in [Table 6-3](#) above.

Dose escalation will be recommended by the DMC and will be determined by the Sponsor's safety committee upon review of the safety data obtained during the DLT evaluation period as well as available data beyond the DLT evaluation period from all patients in the trial. Dose escalation will be allowed when the DMC has recommended the dose and the dosing schedule for the next dose level and the Sponsor's safety committee has approved it.

To better understand the safety, tolerability, PK, pharmacodynamics, or anti-tumor activity of nivatrotamab, up to 10 additional patients in total may be allocated in parallel to dose levels that are considered safe for such allocation (i.e., dose levels at or below the currently investigated one). This could be based on recommendations provided by the DMC. DLT information from patients in such additional cohorts will be taken into account for decisions on the dose level for the next cohort; the dose escalation rules shown in [Table 6-3](#) can still be followed.

When a DLT in such an additional cohort is observed and the updated DLT information on a previously investigated lower dose level leads to decisions that come in conflict with previously taken decisions, the DMC will recommend the dose level for the next cohort. It will be possible to de-escalate from the starting dose, provided it is not disallowed due to toxicity.

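### Section 6.2.1.6 lets the RP2D be declared on activity grounds before the MTD is reached, with no minimum number of DLT-evaluable patients at the chosen level

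*Combined protocol and SAP*

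**What the plan says.** Section 6.2.1.5 lists the formal ends of dose escalation. Apart from the cap of 39 and a starting dose that proves too toxic, there are two. One needs 9 DLT-evaluable patients at the current level and a decision to remain. The other needs 6 with at most 1 DLT, after a higher level has led to de-escalation.

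Section 6.2.1.6 adds a further route. It opens: "If there is evidence that a dose level lower than the MTD (which might not have been reached at this stage) has adequate clinical activity". The evidence may be of several kinds: "whether determined by imaging data, pharmacodynamics endpoints, or predicted efficacious dose". The DMC and the Sponsor's safety committee then "may decide that the RP2D has been determined and that the dose escalation may be stopped". The same section states that "The RP2D cannot exceed the MTD" and that "The selection of the RP2D will be based on pharmacokinetic, pharmacodynamic, safety and efficacy data from Phase 1".

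Section 6.2.1.3 governs how many patients a level holds. In the accelerated stage, "patients will be recruited and treated in single-patient cohorts", with optional expansion by up to 2. That stage ends at dose level 3, or earlier on a DLT or a grade 2 or higher AE not clearly due to progression or intercurrent illness. In the standard stage a cohort may have only 2 evaluable patients if neither had a related grade 3 or higher AE. Section 6.2.1.4 adds that "up to 10 additional patients in total may be allocated in parallel to dose levels" considered safe for this. That is an option, not a requirement at the RP2D.

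**The concern.** The RP2D is part of a primary endpoint of phase 1 and sets the dose for 30 phase 2 patients. The plan's other ways of settling on a dose rest on 6 or 9 evaluable patients, and Appendix 1 regards 9 as the point where the algorithm has roughly converged. The activity route has no such floor. No number appears in the readable text of section 6.2.1.6, section 6.2.2.1, the synopsis, section 11 or Appendix 1.

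The route is also not one of the two BOIN modifications listed in Appendix 1, and the description of the simulations does not mention it. The reported operating characteristics therefore cannot be taken to cover it. The synopsis describes RP2D selection only after the algorithm has been completed, which does not match section 6.2.1.6.

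At stake is a phase 2 that opens at a level whose DLT rate is barely known. The 3-day gap between first doses is stated only for the dose escalation part.

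**Working it through.** **Inputs.** Target DLT rate 28%; overly toxic rate 1.4 × 28% = 39% (Appendix 1). Smallest evaluable numbers per level: 1, 2 or 3 (section 6.2.1.3). Comparison number: 6 (sections 4.5 and 6.2.1.5). Phase 2 size: 30 (section 6.3.1). The illustrations use a true DLT rate of 40%, a rounded version of the plan's 39%.

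**The plan's own figures reproduce.** Table 11-1 is 1 − (1 − p)^n. For p = 30% it gives 65.7%, 88.2%, 96.0% and 100.0% at n = 3, 6, 9 and 30 (stated 66%, 88%, 96%, 100%), and all 24 cells agree. The BOIN boundaries recompute to 0.2285 and 0.3344 (stated 0.229 and 0.334) and give the escalate, remain and de-escalate rows of Table 6-3. Table 11-1 does not show n = 1 or 2.

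**Chance of a clean result at a toxic level.** This is (1 − p)^n. The two-sided exact 95% upper limit after 0 of n is 1 − 0.025^(1/n).

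| n | No DLT, p = 40% | No DLT, p = 39% | Upper limit after 0 of n |
|---|---|---|---|
| 1 | 60% | 61% | 98% |
| 2 | 36% | 37% | 84% |
| 3 | 22% | 23% | 71% |
| 6 | 5% | 5% | 46% |

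For n = 1 and n = 2 these probabilities are upper bounds. Staying at one patient also requires no qualifying grade 2 or higher AE, and a two-patient cohort also requires no related grade 3 or higher AE.

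**Consequence in phase 2.** If a 39% rate carried over, 0.39 × 10 = 3.9 of the first 10 patients and 0.39 × 30 = 11.7 of all 30 would be expected to have a DLT-type event.

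**Effect of requiring 6 evaluable patients with at most 1 DLT (p = 40%).** Multiply the chance of a clean start by the chance of at most 1 DLT among the patients added.

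- From 1: 0.600 × (0.6^5 + 5 × 0.4 × 0.6^4) = 0.600 × 0.337 = 20%
- From 2: 0.360 × (0.6^4 + 4 × 0.4 × 0.6^3) = 0.360 × 0.475 = 17%
- From 3: 0.216 × (0.6^3 + 3 × 0.4 × 0.6^2) = 0.216 × 0.648 = 14%

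**Why the DLT threshold must be stated too.** Table 6-3 calls for de-escalation at n = 6 only from 3 DLTs, so a rule of merely not de-escalating would admit 2 of 6. From 0 of 3 that gives 0.216 × 0.936 = 20%, hardly below the starting 22%.

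**The case against.** The route is not unguarded. It needs evidence of adequate activity and the decision of two bodies. Selection draws on all phase 1 data, including exposure-response analyses, so higher levels already dosed also inform the safety of the chosen one. Disallowed levels are out of reach. Phase 2 has a DMC meeting once the 10th patient completes Cycle 1, SAEs are shared with the DMC until then, patients are hospitalised for 48 hours in the first two cycles, and section 6.2.5 provides holds. Appendix 1 itself describes the low levels as unlikely to be therapeutic, so a one-patient level is an improbable choice.

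All of this stands, and it rules out stronger readings that a reader might infer:

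- That any level already dosed could become the RP2D. The activity condition and the disallowed levels prevent that.
- That 30 patients would be treated on the evidence of 1 to 3. Those are worst-case counts at the chosen level, not the whole evidence, and a review comes after the 10th patient.
- That the default under which "the RP2D will be the highest dose administered that does not exceed the MTD" belongs to the same route. It applies when results are not compelling and follows the sentence about the completed algorithm; the activity route requires positive evidence.

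What does not stand is that these limits supply the missing minimum. The MTD bound cannot be verified while the MTD is unknown. Disallowing in Table 6-3 is not applicable at 2 patients and needs 3 DLTs at 3. The phase 2 meeting follows 14 days of treatment in the 10th patient, against a 28-day DLT window, and neither it nor the holds carries a numerical DLT boundary.

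**Conclusion.** The gap is real. For an RP2D declared on activity before the MTD is reached, the protocol sets no minimum number of DLT-evaluable patients at the chosen level. Two or three would satisfy the text, or one below dose level 3 without a qualifying AE or DLT. At those counts a clean record cannot separate an acceptable level from one that the plan calls overly toxic: every upper limit lies far above 39%.

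The size rests on an assumed true DLT rate of 40%, on evaluating the chosen level by itself, and, for the phase 2 counts, on the phase 1 rate carrying over. The percentages are conditional on such a level being chosen; they do not estimate how often the route would be used. The DMC charter is not among the documents. A minimum stated there would narrow the point, but the protocol would still need to refer to it.

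**What to change.** In section 6.2.1.6, state that an RP2D declared by the activity route needs at least 6 DLT-evaluable patients at that level with at most 1 DLT, the count already used in section 6.2.1.5. Alternatively, the sponsor states and justifies another minimum and threshold. Any shortfall is filled from the up to 10 additional patients of section 6.2.1.4, who are already inside the cap of 39. Bring the synopsis into line. Six is borrowed from the plan; its existing 6-patient stop also requires de-escalation from a higher level, which could not apply before such a level has been tested.

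**Cost.** The change takes one or two sentences and leaves the cap unchanged. Starting from 3, 2 or 1 evaluable patients, it uses 3, 4 or 5 of the budgeted places. At 39 patients over 18 months (39/18 = 2.17 per month), 3 to 5 patients take roughly 3/2.17 = 1.4 to 5/2.17 = 2.3 months to accrue, plus one further 28-day window before phase 2. The protocol gives 18 months as a minimum, so accrual could be slower. Appendix 1 expects 18 to 23 patients in total, so room under the cap is likely.

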## 6.2.2 Phase 2: Dose Expansion

### 6.2.2.1 Dose Regimen

In phase 2, the RP2D identified in phase 1 will be used (in order to assess the long-term safety and anti-tumor activity of nivatrotamab at this dose). It will be based on a review of the available safety information, including AEs and safety laboratory values, relevant PK data, and observations made after the end of the DLT evaluation period.

### 6.2.3 Definition of Dose-limiting Toxicity

DLTs include the following events:

Clinically significant AE (CTCAE version 5.0) or a significant laboratory abnormality (as defined below) that occurs during the DLT assessment period, excluding toxicities clearly related to disease progression or intercurrent illness. The established external, independent DMC will evaluate relatedness of an event in order for it to qualify for a DLT or not.

DLT criteria will be categorized as follows:

1. Thrombocytopenia grade 3 with clinically significant bleeding and neutropenia (i.e., myelosuppression) > grade 3, excluding neutropenia lasting <7 days and
2. Non-hematological toxicities  $\geq$  grade 3, defined as
  - a. Grade 3 non-hematological laboratory abnormalities requiring medical intervention, which are not mentioned in the list of exceptions below.
  - b. Any non-hematological AE of  $\geq$  grade 3 that is not mentioned in the list of exceptions below.
3. Death occurring during DLT evaluation period, not related to disease progression or complications or intercurrent illness as determined by the DMC
4. Injection site reaction  $\geq$  grade 3
5. Dose delay of >21 days (failure to recover from any toxicity, which results in delayed dosing of the subsequent dose)
6. CRS grade 3 or higher
7. Immune effector cell-associated neurotoxicity syndrome (ICANS) grade 3 or higher
8. Peripheral sensory neuropathy grade 4
9. Peripheral sensory neuropathy grade 3 with no sign of clinical improvement within 21 days as evaluated by the investigator.
10. Pain grade 3 or higher lasting 24 h or more despite optimal analgesic therapy administered according to the local standard of care
11. Febrile neutropenia

12. Any AST/ALT and bilirubin elevation meeting Hy's law criteria (a,b,c and d)
  - a. ALT or AST elevation  $> 3 \times$  upper limit of normal (ULN)
  - b. Total bilirubin elevation  $> 2 \times$  ULN
  - c. Absence of initial findings of cholestasis
  - d. No other reason to be found i.e. due to infection (i.e. hepatitis), liver disease or other drug effect

### **List of exceptions: non-hematological exceptions**

The following AEs will not constitute DLTs (however, they should be reported as AEs/SAEs according to the reporting guidelines).

- Grade 3 laboratory values considered not clinically significant
- Grade 3 headache, nausea, diarrhea, and vomiting, persisting for  $< 48$  h (with adequate supportive care)
- Grade 3 elevations of ALT/AST  $\leq 8 \times$  ULN or baseline ALT/ AST (in case baseline above ULN at study entry) improved to  $<$  grade 3 within 14 days
- Grade 3 hypertension lasting  $< 48$  h
- Grade 3 Fever lasting  $< 72$  h
- Grade 3 Fatigue lasting  $< 7$  days

AEs that are self-limited and resolve within a short time frame will not constitute DLTs; however, they should be reported as AEs/SAEs according to the reporting guidelines.

For the purpose of dose escalation, DLTs will be collected and assessed throughout Cycles 1 and 2, covering a treatment period of 4 weeks. This will allow for the evaluation of up to 3 investigational medicinal product (IMP) administrations.

DLTs must be entered in the clinical AE report form and reported from the site to the Sponsor within 24 h of the Investigator's first knowledge of the event. In case any of the side effects mentioned in the DLT definitions occur during Cycles 2 to 5 in Phase 1, these will be discussed at the first upcoming preplanned DMC meeting, and the Sponsor's safety committee will evaluate the DMC recommendations for further dosing.

#### **6.2.4 Dose Modifications**

Patients developing grade 3 toxicity not meeting the DLT criteria, that is not resolved/decreased to a lower grade within 36 h, will have treatment paused until toxicity is maximum grade 2 or returned to baseline value at study entry (e.g. lab values).

If the grade 3 toxicity is considered clinically significant by the investigator, patients will be planned for continued dosing at one lower dose level (dose level -1). No dose modification indicated for toxicities grade 1-2.

### **6.2.5 Trial Stopping Rules**

If any of the following occur, administration of the IMP will be stopped, and recruitment will be put on hold at least temporarily until DMC feedback is received to confirm if the trial can continue:

- 1) One or more patients experience unexpected, sudden death during the treatment period
- 2) Treatment related death before the EOT visit
- 3) SAEs or frequency of AEs that, in the judgement of the Sponsor, are deemed to warrant immediate review by the DMC.
- 4) Any other safety finding assessed as related to nivatrotamab that, in the opinion of the DMC or Sponsor, contraindicates further dosing of trial patients.

If any of these occur, an immediate cumulative review of safety data with focus on the SAE/ AE in question will be conducted by the DMC to determine whether dosing and further recruitment should be resumed, the protocol modified, or whether the trial should be discontinued. Review and approval of the Sponsor Safety Committee is required for resumption of the trial in case the trial is interrupted due to one of the above-mentioned safety findings.

When applicable, regulatory authorities and ECs/IRBs will be notified of actions taken with the trial.

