### 6.2.11 End of Treatment Visit

At both phase 1 and phase 2, an “end of treatment” (EOT) visit should be made when the patient completes treatment or permanently discontinues the IMP. The EOT visit will be performed at the time of discontinuation, within 30 days after the last IMP dose and prior to initiation of any new anticancer treatment. In case of premature study discontinuation, the EOT visit should be performed immediately. The reason for discontinuation from treatment must be documented in the eCRF.

The EOT visit will include the following assessments: physical examination, vital signs and body weight, ECOG performance score, neurological examination, recording of concomitant medication and concurrent procedures, safety laboratory assessments (hematology, coagulation and clinical chemistry), HCG test (for females of childbearing potential), anti-drug antibodies, AEs/SAEs, urinalysis, and CT scanning of the primary tumor site (if the last prior tumor assessment was >6 weeks from date of the EOT visit).

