### 6.3.3 Premature Discontinuation of Treatment

#### 6.3.3.1 Treatment Discontinuation Criteria

A patient should be discontinued from treatment with the IMP if any of the following situations occur:

- Any DLT (see section 6.2.3)
- Disease progression - confirmed PD (confirmed immune PD [iCPD]) or as clinically judged by the Investigator
- Patients with suspected progression, i.e., unconfirmed PD (unconfirmed immune PD [iUPD]), are allowed to continue treatment if they are considered to be clinically stable in the opinion of the Investigator until confirmatory radiological assessment (CT scan) is performed.
- In case of decreased ejection fraction (EF) of grade 3 (EF, 39%–20% or  $\geq 20\%$  drop from baseline), and the event is considered treatment-related.
- Investigator's decision for medical or safety reasons
- If the patient receives prohibited anti-tumor therapy/procedures during the trial
- Patient chooses to withdraw from the therapy at any time
- Pregnancy

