### 9.5.2 Serious Adverse Events Reporting

Serious AEs should be reported from signing the informed consent until 30 days after the last IMP administration.

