### 11.4.3 Adverse Events

The overall observation period for AEs will be divided into 3 parts:

- Pre-treatment period: From the day of the patient’s informed consent to the day before the first dose of nivatrotamab
- On-treatment period: From the day of the first dose of nivatrotamab to 30 days after the last dose of nivatrotamab
- Post-treatment period: From 31 days after the last dose of nivatrotamab and thereafter

If dates are incomplete in a way that clear assignment to pre-, on-, post-treatment period cannot be made, the respective data will be assigned to the on-treatment period.

Additional analyses and presentations will be included in the SAP.

AEs will be presented descriptively in summary tables and listings.

AEs will be regarded as Treatment-emergent AEs (TEAEs) if they occur after the start of the first IMP administration.

A TEAE is defined as an AE that emerges during treatment having been absent pre-treatment (i.e., has onset on or after the first dose of study treatment).

AEs with onset during the pre- and post-treatment periods will be listed. AEs with onset during the on-treatment period will be summarized as follows:

- Summaries of AEs by MedDRA SOC and PT will be presented for all TEAEs, related TEAEs, CTCAE grade 3 or higher TEAEs, related CTCAE grade 3 or higher TEAEs, injection-related TEAEs, SAEs, related SAEs, CTCAE grade 3 or higher SAEs, related CTCAE grade 3 or higher SAEs, TEAEs leading to treatment discontinuation, and AEs leading to death.

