## 15 PREMATURE TERMINATION OF THE TRIAL

### 15.1 Sponsor Criteria for Pausing Patient Enrolment

Enrolment will be paused if one of the following criteria is met:

- One or more patients experience unexpected, sudden death during the treatment period
- SAEs or frequency of AEs that, in the judgement of the Sponsor, are deemed to warrant immediate review by the DMC.
- One or more patients experience treatment-related death before EOT visit

If an above-mentioned criterion is met, the DMC will review the safety results and determine how to proceed as described in section [9.9.3](#).

Patients already included at the time of clinical trial pause, will continue in the clinical trial but further dosing will be postponed until a decision has been reached by the DMC.

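### The automatic hold for a treatment-related death is cut off at the EOT visit, so its reach after the last dose varies from about 0 to 30 days with visit scheduling

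*Combined protocol and SAP*

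**What the plan says.** Section 6.2.5 lists four events that stop IMP administration and put recruitment on hold until the DMC has responded. Rule 2 is "Treatment related death before the EOT visit". Section 15.1, on pausing enrolment, has the matching criterion "One or more patients experience treatment-related death before EOT visit", and adds that for patients already in the trial "further dosing will be postponed until a decision has been reached by the DMC".

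The EOT visit is defined in section 6.2.11: "The EOT visit will be performed at the time of discontinuation, within 30 days after the last IMP dose". It is triggered by completing treatment or by stopping IMP permanently. A further sentence reads "In case of premature study discontinuation, the EOT visit should be performed immediately". Section 6.3.3.1 makes any DLT a reason to stop IMP.

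Two other safety windows are fixed relative to the last dose. Section 11.4.3 defines "On-treatment period: From the day of the first dose of nivatrotamab to 30 days after the last dose of nivatrotamab". Section 9.5.2 states "Serious AEs should be reported from signing the informed consent until 30 days after the last IMP administration".

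The other three rules in 6.2.5 are:

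- Rule 1: an unexpected, sudden death in the treatment period, a term the rule does not define.
- Rule 3: SAEs or AE frequencies that the Sponsor judges to need immediate DMC review.
- Rule 4: any other related finding that the DMC or Sponsor thinks contraindicates further dosing.

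**The concern.** The EOT visit is a scheduling event. Two patients could die of the same drug-related toxicity on the same day after their last dose. If one had not yet had the visit, a hold is required; if the other had, it is discretionary. Nothing in the protocol explains why the trigger should depend on this.

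The dependence also tends to run in an unhelpful direction. A DLT requires IMP to be stopped, stopping brings the EOT visit, and the visit closes the automatic trigger. Patients stopped for toxicity therefore tend to have the shortest cover, although a delayed related death is a plausible worry in that group.

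What is at stake is the dosing of other patients. A hold postpones their doses until the DMC has decided. The Sponsor's written confirmation of each new patient (6.2.9.1 and 6.2.9.2) controls new starts only and does not pause anyone already on treatment.

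**Working it through.** The plan gives no figure to reproduce, so the check is day arithmetic and a reading of the rules side by side.

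**Inputs**

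- Trigger closes at the EOT visit: 6.2.5 rule 2 and 15.1.
- EOT visit at discontinuation, no minimum interval, at most 30 days after the last dose: 6.2.11.
- Comparison window of 30 days after the last dose: 9.5.2 and 11.4.3.
- Cycle length 14 days (6.2.1.1); permitted treatment delay up to 3 weeks, or 21 days (7.1.2.3).

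**Step 1: length of the gap.** Uncovered days = 30 − EOT day, counting days from the last dose.

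| EOT day | Uncovered days |
|---|---|
| 0 | 30 − 0 = 30 |
| 7 | 30 − 7 = 23 |
| 14 | 30 − 14 = 16 |
| 21 | 30 − 21 = 9 |
| 30 | 30 − 30 = 0 |

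These EOT days are illustrative; the documents do not give their distribution. The flow charts also attach a 4-day allowance to the visit, without a clear anchor. It could move a visit by a few days and does not change the finding.

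**Step 2: what can trigger a hold inside the gap.** Take a related death after the EOT visit and within 30 days of the last dose.

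- Rule 1 applies only if the death is both unexpected and sudden, and if the treatment period is read to extend past the EOT visit. A patient who declines over days after a DLT is unlikely to meet it.
- Rule 2 does not apply.
- Rules 3 and 4 can apply, but each turns on the judgement of the Sponsor or the DMC.
- In phase 1, a death within the 28-day DLT period that is not due to progression or intercurrent illness is itself a DLT (6.2.3, item 3). That feeds the dose decision in Table 6-3, which is not a hold. Table 6-3 counts patients with DLTs, so a death in a patient already counted adds 0.

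**Step 3: check of the replacement window.** A plain 30-day rule could remove cover that exists now. If one dose is given per 14-day cycle (an assumption; the dosing table is redacted), a patient on the longest permitted delay may be 14 + 21 = 35 days past the last dose with no EOT visit yet. Rule 2 covers that patient today, but a plain 30-day limit would not, because 35 > 30. Covering the later of 30 days and the EOT visit keeps this cover and brings the uncovered part of the 30-day window to 0 for everyone.

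**The case against.** The strongest case against is that the practical gap is narrow. It needs a related death, after the EOT visit, within 30 days, outside rule 1, that neither the Sponsor nor the DMC thinks worth a hold. Rules 3 and 4 lead to the same hold and the same immediate cumulative review. Every death is an SAE (9.6.4) and reaches the Sponsor within 24 hours (9.7). Significant safety issues go promptly to the DMC (9.9.2). During phase 1 and up to the phase 2 DMC meeting, all SAEs are shared with the DMC and unplanned meetings can be called (9.9.3). Rule 2 itself depends on a relatedness judgement.

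Most of this stands, and it limits the weight of the point. It does not remove it. Once relatedness is accepted, rule 2 leaves no further discretion, whereas rules 3 and 4 do. The 9.9.3 arrangements are also stated only up to the phase 2 DMC meeting, which follows the tenth phase 2 patient's Cycle 1; 30 patients are planned.

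Four stronger readings are tempting, and the documents do not support them.

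- *The protocol contradicts itself.* It does not. The 30 days is a window for reporting and analysis and is never stated as the stopping-rule window. This is a design weakness.
- *A DLT always brings an immediate EOT visit.* The sentence on immediacy concerns premature study discontinuation, while a DLT ends treatment; withdrawal from the trial is handled separately (6.3.4). What applies to DLT patients is a visit at the time of discontinuation, within 30 days of the last dose. This tends to be early but is not fixed.
- *Such a death simply waits for the next planned DMC meeting.* Section 6.2.3 says this of DLT-type events during Cycles 2 to 5 of phase 1. It does not displace 6.2.5 or the unplanned meetings, and it is not written for deaths after treatment has ended.
- *A typical share of the window is uncovered.* Any such percentage needs an assumed stopping day and an assumed anchor for the 4-day allowance. Only the 0 to 30 day range comes from the text.

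**Conclusion.** The point holds as a limited design weakness. The automatic hold for a treatment-related death reaches between about 0 and 30 days past the last dose, depending on when the EOT visit happens, and tends to be short for patients stopped for a DLT. Inside the remaining days a hold rests on Sponsor or DMC judgement, except for deaths that rule 1 may catch.

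The gap is in the mandatory trigger. Data capture is unaffected, and no endpoint or analysis changes. The event should be rare: section 4.6 reports no fatal AE in the first-in-human trial. The documents give no rate of related death, so the frequency cannot be computed. The conclusion rests on the protocol text alone. The DMC charter was not available and may contain a further trigger, in which case the change would only bring the protocol into line with it.

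**What to change.** In 6.2.5 rule 2 and the third criterion of 15.1, replace the EOT cut-off with: *within 30 days after the last dose of IMP, regardless of when the EOT visit is held, or before the EOT visit, if later*. This aligns the trigger with the windows in 9.5.2 and 11.4.3 and keeps the cover that patients on a dose delay have now.

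The cost is wording in two sections at the next amendment, plus an occasional extra temporary hold and ad hoc DMC review. Some deaths in the added days may follow a new anticancer treatment, which makes relatedness harder to judge. The rule would still apply only to deaths judged treatment-related. The change is a cheap improvement and worth making.
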